### **Expectedness assessment**

Since KAF156 and LUM-SDF will be administered to the patients on the same day, it would only be possible to assess the suspectedness of the reported SAEs to the combination (i.e., KAF156 and LUM-SDF). Hence, the expectedness of the reported SAEs will also be assessed for the combination. KAF156 and LUM-SDF have separate Investigator Brochure (IB) and the respective reference safety information (RSI) will be used. If the reported SAE/s is/are listed in the RSI of either of the product's IB, those will be considered as expected adverse events to the combination product (i.e., KAF156 and LUM-SDF) for reporting purposes. RSI in the LUM-SDF IB is based on the safety profile of Coartem®.

### **7.2.2 SAE reporting**

To ensure patient safety, every SAE, regardless of causality, occurring after the patient has provided informed consent and until 30 days after the last study visit must be reported to Novartis safety within 24 hours of learning of its occurrence. Any SAEs experienced after the 30 day period after the last study visit should only be reported to Novartis safety if the investigator suspects a causal relationship to study treatment.

All follow-up information for the SAE including information on complications, progression of the initial SAE and recurrent episodes must be reported as follow-up to the original episode within 24 hours of the investigator receiving the follow-up information. An SAE occurring at a different time interval or otherwise considered completely unrelated to a previously reported one must be reported separately as a new event.

Information about all SAEs (either initial or follow up information) is collected and recorded in English in the electronic Serious Adverse Event (eSAE) Form within the Oracle Clinical/Remote Data Capture (OC/RDC) system (wherever available and/or feasible) or on the paper Serious Adverse Event Report Form that should be used as back-up, especially in case where there is no feasibility of the use of eSAE form. The Investigator must assess the relationship to the study treatment (KAF156/lumefantrine combination or Coartem®).

SAEs (initial and follow-up) that are recorded electronically in the OC/RDC system should be entered, saved and e-signed within 24 hours of awareness of the SAE or changes to an existing SAE. These data will automatically be submitted to Novartis Chief Medical Office and Patient

Safety (CMO&PS) immediately after investigator signature or 24 hours after entry, whichever occurs first.

Follow-up information is submitted as instructed in the investigator folder. Each re-occurrence, complication, or progression of the original event must be reported as a follow-up to that event regardless of when it occurs. The follow-up information should describe whether the event has resolved or continues, if and how it was treated, and whether the patient continued or withdrew from study participation.

If the SAE is not previously documented in the Investigator Brochure(s) (IB) or Package Insert (new occurrence) and is thought to be related to the study treatment a CMO&PS Department associate may urgently require further information from the investigator for Health Authority reporting. Novartis may need to issue an Investigator Notification (IN) to inform all investigators involved in any study with the same study treatment that this SAE has been reported. Suspected Unexpected Serious Adverse Reactions (SUSARs) will be collected and reported to the competent authorities and relevant ethics committees in accordance with European Union (EU) Guidance 2011/C 172/01 or as per national regulatory requirements in participating countries.

### 7.3 Liver safety monitoring

To ensure patient safety and enhance reliability in determining the hepatotoxic potential of an investigational drug, a standardized process for identification, monitoring and evaluation of liver events has to be followed.

The following two categories of abnormalities/adverse events have to be considered during the course of the study (irrespective of whether classified/reported as (S)AE):

- Liver laboratory triggers, which will require repeated assessments of the abnormal laboratory parameter.
- Liver events, which will require close observation, follow-up monitoring, completion of the specific liver CRF pages and reported as SAE ([Section 7.2.2](#)).

Please refer to [Table 14-1 in Appendix 2](#) for complete definitions of liver laboratory triggers and liver events.

[figure not shown]
Every liver laboratory trigger or liver event as defined in [Table 14-1 of Appendix 2](#) should be followed up by the investigator or designated personal at the trial site as summarized below. Detailed information is outlined in [Table 14-2 in Appendix 2](#).

For the liver laboratory trigger:

- Repeating the liver function test (LFT) within 24 hours to confirm elevation.  
Repeat laboratory tests must be entered on the appropriate unscheduled local laboratory CRF page.
- If the elevation is confirmed, close observation of the patient will be initiated, including consideration of treatment discontinuation if deemed appropriate.

For the liver events:

- Repeating the LFT to confirm elevation as appropriate.

- Discontinuation of the investigational/study drug if appropriate.
- Hospitalization of the patient if appropriate.
- A causality assessment of the liver event via exclusion of alternative causes (e.g., disease, co-medications).
- Report to Novartis as SAE.
- An investigation of the liver event which needs to be followed until resolution.

These investigations can include serology tests, imaging and pathology assessments, hepatologist's consultancy, based on pre-defined checklist. All follow-up information, and the procedures performed must be recorded on appropriate CRF pages, including the liver event overview CRF pages.

#### 7.4 Renal safety monitoring

The following two categories of abnormal renal laboratory values have to be considered during the course of the study:

- Serum event:
  - confirmed (after  $\geq 24$ h) increase in serum creatinine of  $\geq 25\%$  compared to baseline during normal hydration status
- Urine event
  - new onset ( $\geq 1+$ ) proteinuria; confirmed by doubling in the urinary albumin-creatinine ratio (ACR) or urinary protein-creatinine ratio (uPCR) (if applicable)
  - new onset ( $\geq 1+$ ), hematuria or glycosuria

Every renal laboratory trigger or renal event as defined in [Table 16-1 in Appendix 4](#) should be followed up by the investigator or designated personnel at the trial site as summarized in [Appendix 4](#).

#### 7.5 Cardiac Safety Monitoring

To ensure patient safety and fully characterize the cardiovascular safety of the investigational drug, a standardized process for identification, monitoring and evaluation of cardiac events is followed.

The following categories of notable ECG changes will be assessed during the course of the study (irrespective of whether classified/reported as (S)AE):

- QTcF increase from pretreatment baseline  $\geq 60$  ms (QTcB for children  $\leq 6$  years)
- QTcF  $> 500$  ms (QTcB for children  $\leq 6$  years)

Resting heart rate:

- ECG of HR  $< 50$ /min with  $> 25\%$  decrease from pretreatment baseline or
- HR  $< 50$ /min associated with symptoms

Cardiac rhythm:

- Any cardiac arrhythmia associated with hemodynamical compromise
- Sustained ventricular tachycardia  $\geq 30$  sec, or ventricular fibrillation

Every cardiac event as defined in [Table 15-1 in Appendix 3](#) should be appropriately documented in the eCRF (both AE and SAE) and followed up by the investigator or designated personnel at the trial site as summarized in [Appendix 3](#).

## 7.6 Reporting of study treatment errors including misuse/abuse

Medication errors are unintentional errors in the prescribing, dispensing, administration or monitoring of a medicine while under the control of a healthcare professional, patient or consumer (European Medicines Agency (EMA) definition).

Misuse refers to situations where the medicinal product is intentionally and inappropriately used not in accordance with the protocol.

Abuse corresponds to the persistent or sporadic, intentional excessive use of a medicinal product, which is accompanied by harmful physical or psychological effects.

Study treatment errors and uses outside of what is foreseen in the protocol will be collected in the dose administration record (DAR) eCRF irrespective of whether or not associated with an AE/SAE and reported to Safety only if associated with an SAE. Misuse or abuse will be collected and reported in the safety database irrespective of it being associated with an AE/SAE.

**Table 7-1 Guidance for capturing the study treatment errors including misuse/abuse**

Treatment error type	Document in Dose Administration (DAR) eCRF (Yes/No)	Document in AE eCRF	Complete SAE form
Unintentional study treatment error	Yes	Only if associated with an AE	Only if associated with an SAE
Misuse/Abuse	Yes	Yes	Yes, even if not associated with a SAE

## 7.7 Pregnancy reporting

To ensure patient safety, each pregnancy occurring after signing the informed consent must be reported to Novartis within 24 hours of learning of its occurrence. The pregnancy should be followed up to determine outcome, including spontaneous or voluntary termination, details of the birth, and the presence or absence of any birth defects, congenital abnormalities, or maternal and/or newborn complications.

Pregnancy must be recorded on the Pharmacovigilance Pregnancy Form and reported by the investigator to the local/regional Novartis CMO&PS Department. Pregnancy follow-up should be recorded on the same form and should include an assessment of the possible relationship to the study treatment.

Any SAE experienced during the pregnancy and unrelated to the pregnancy must be reported on an eSAE form/paper SAE form (as applicable).

Pregnancy outcomes should be collected for the female partners of any males who took study treatment in this study. Consent to report information regarding these pregnancy outcomes should be obtained from the female partner.

## **8 Data review and database management**

### **8.1 Site monitoring**

Before study initiation, at a site initiation visit or at an investigator's meeting, a Novartis representative will review the protocol and eCRFs with the investigators and their staff. During the study, the field monitor will visit the site regularly to check the completeness of patient records, the accuracy of entries on the eCRFs, the adherence to the protocol and to Good Clinical Practice (GCP), the progress of enrollment, and to ensure that study drug is being stored, dispensed, and accounted for according to specifications. Key study personnel must be available to assist the field monitor during these visits.

The investigator must maintain source documents for each patient in the study, consisting of case and visit notes (hospital or clinic medical records) containing demographic and medical information, laboratory data, electrocardiograms, and the results of any other tests or assessments. All information on eCRFs must be traceable to these source documents in the patient's file. The investigator must also keep the original informed consent form signed by the patient (a signed copy is given to the patient).

The investigator must give the monitor access to all relevant source documents to confirm their consistency with the eCRF entries. Novartis monitoring standards require full verification for the presence of informed consent, adherence to the inclusion/exclusion criteria, documentation of SAEs, and the recording of data that will be used for all primary and safety variables. Additional checks of the consistency of the source data with the eCRFs are performed according to the study-specific monitoring plan. No information in source documents about the identity of the patients will be disclosed.

### **8.2 Data collection**

Designated investigator staff will enter the data required by the protocol into the Electronic Case Report Forms using fully validated software that conforms to 21 US Code of Federal Regulations (CFR) Part 11 requirements. Designated investigator site staff will not be given access to the EDC system until they have been trained. Automatic validation programs check for data discrepancies and, by generating appropriate error messages, allow the data to be confirmed or corrected. The Investigator must certify that the data entered into the Electronic Case Report Forms are complete and accurate. After database lock, the investigator will receive a CD-ROM or paper copies of the subject data for archiving at the investigational site.

All data captured for this study will have an external originating source (either written or electronic), the eCRF is not considered as source.

Designated investigator staff will enter the data required by the protocol into the OC/RDC system. Designated investigator site staff will not be given access to the system until they have been trained.

Automatic validation procedures within the system check for data discrepancies during and after data entry and, by generating appropriate error messages, allow the data to be confirmed or corrected online by the designated investigator site staff. The Investigator must certify that the data entered into the electronic Case Report Forms are complete and accurate. After

database lock, the investigator will receive copies of the patient data for archiving at the investigational site.

### **8.3 Data management and quality control**

Novartis staff (or Contract Research Organization (CRO) working on behalf of Novartis) review the data entered into the CRFs by investigational staff for completeness and accuracy and instruct the site personnel to make any required corrections or additions. Queries are sent to the investigational site using an electronic data query. Designated investigator site staff is required to respond to the query and confirm or correct the data. If the electronic query system is not used, a paper Data Query Form will be faxed to the site. Site personnel will complete and sign the faxed copy and fax it back to Novartis staff or designee that will make the correction to the database. The signed copy of the Data Query Form is kept at the investigator site.

Concomitant medications entered into the database will be coded using the WHO Drug Reference List, which employs the Anatomical Therapeutic Chemical (ATC) classification system. Concomitant procedures, non-drug therapies and adverse events will be coded using the Medical dictionary for regulatory activities (MedDRA) terminology.

For those laboratory samples that will be processed centrally the results will be sent electronically to Novartis (or a designated CRO).

ECG readings will be processed centrally and the results will be sent electronically to Novartis (or a designated CRO).

Randomization codes and data about all study drug(s) dispensed to the patient will be tracked using an Interactive Response Technology (IRT). The system will be supplied by a vendor, who will also manage the database. The database will be sent electronically to Novartis (or a designated CRO).

[figure not shown]
The occurrence of relevant protocol deviations will be determined for each part separately. After these actions have been completed and the database has been declared to be complete and accurate, it will be locked and the treatment codes will be unblinded and made available for data analysis for each part. Any changes to the database after that time can only be made after written agreement by Novartis Development management.

### **8.4 Data Monitoring Committee**

An independent Data Monitoring Committee (DMC) will be established for this study to review patient safety at several time points. The DMC can recommend to stop the study or a specific cohort in case of serious safety observations which can include a non-acceptable rate of early treatment failures. The DMC will consist minimally of an external clinician with expertise in tropical diseases and external statistician. Regular formal interim assessment to review patient safety will be performed during the study as specified in the DMC charter.

Additional ad-hoc safety review may be requested by DMC or Novartis if needed.

Details of safety analyses will be specified in the analysis plan for the DMC. The DMC will make recommendations to Novartis on any safety issues that are deemed relevant.

The DMC is accountable to the Sponsor for appropriate monitoring of the study data. Although the DMC may make recommendations to the Sponsor about changes in the conduct of the study, final decisions will be made by Novartis Clinical Development senior management. In the case of early termination, consultation with Health Authorities may be required. Further details of the DMC's composition, organization and responsibilities will be described in the DMC charter.

## 9 Data analysis

Statistical analyses for PK Run-in Part, Part A and Part B will be performed separately. For key efficacy and safety outcomes, pooled analysis will be performed by pooling Part B with corresponding cohorts in Part A. Unless described separately otherwise, same statistical method will be used for separate analysis and pooled analysis.

For each cohort in Part B, a corresponding cohort in Part A will exist with matching dose and regimen. For statistical analyses and clinical study reporting, treatment group name, instead of cohort number, will be used for both parts and the pooled analysis which will include only those treatment groups with patients in both parts. The following treatment groups will be used (doses for KAF156 in Part A may be adapted according to [Table 3-1](#)):

- KAF156 400 mg/LUM-SDF 960 mg QD 1 day
- KAF156 800 mg/LUM-SDF 960 mg QD 1 day
- KAF156 400 mg/LUM-SDF 960 mg QD 2 days
- KAF156 200 mg/LUM-SDF 480 mg QD 3 days
- KAF156 400 mg/LUM-SDF 480 mg QD 3 days
- KAF156 400 mg/LUM-SDF 960 mg QD 3 days
- Coartem®

Efficacy data from the PK Run-in Part will not be pooled with the data from other cohorts. The PK analysis will be performed separately for this cohort.

Any data analysis carried out independently by the investigator should be submitted to Novartis before publication or presentation.

### 9.1 Analysis sets

#### Randomized set

All patients who are randomized.

#### Full analysis set (FAS)

FAS will be comprised of all patients from Randomized set who take at least one dose of study treatment during the treatment period and whose baseline parasitaemia count is greater than 0. Following the intent-to-treat principle, patients will be analyzed according to the treatment group assigned to at randomization.

## Safety set (SS)

Safety set includes all patients who take at least one dose of study drug during the treatment period. Patients will be analyzed according to treatment received. Full details will be described in the statistical analysis plan (SAP).

## Per-protocol set (PPS)

Per-protocol set will be comprised of patients in FAS who

- did not have any important protocol deviations
- took at least 80% of randomized study medication(s). If a patient vomited the original dose but did not vomit the replacement dose, the patient is considered as taking the dose of study medication. Except for patients who are assigned to Coartem® cohort, this requires that all patients take all KAF156 and LUM-SDF dosages as assigned
- did not take other antimalarial medications prior to Day 29 for reasons other than rescue medication given for signs and symptoms of infection with *P. falciparum* or unsatisfactory therapeutic effect, and
- met at least one of the following criteria: (a) classified as treatment failure before Day 8 (see [Section 6.5.8](#)), (b) absent from parasitaemia at Day 29 or later, or (c) had valid PCR evaluations at baseline and at the time point with parasitaemia if parasitaemia is present at Day 8 or later.

Important protocol deviations for exclusion from PPS will be identified by the clinical team before database lock for each part.

## PK analysis set

All subjects in the safety analysis set who had evaluable pharmacokinetic parameter data.

## 9.2 Patient demographics and other baseline characteristics

Demographic data and baseline disease characteristics will be descriptively presented and tabulated (n, mean, standard deviation, median, minimum, and maximum for continuous variables; n and percent for categorical variables) per treatment group, as well as overall, using the FAS and PPS.

## 9.3 Treatments

All analyses in this section will be performed using the safety set.

### 9.3.1 Study treatment

Number and percentage of doses taken will be presented by treatment group and drug (KAF156, LUM-SDF, or Coartem®). The percentage will be calculated based on the planned number of doses per treatment group. Percentage of patients with study drug vomiting and dose replacement will be presented by treatment group. Average daily dosage and total dosage (in mg) of each drug (KAF156, LUM-SDF, Coartem®) will be summarized by treatment group.

### 9.3.2 Prior and concomitant medication

Medications will be identified using the Novartis drug and therapy dictionary (NovDTD) including Anatomical Therapeutic Chemical (ATC) code.

Prior and concomitant medications will be summarized by treatment group in separate tables. Concomitant rescue and other anti-malarial medications will also be summarized by treatment group. Medications will be presented in alphabetical order, by ATC codes and grouped by anatomical main group (the first level of the ATC codes). Tables will also show the overall number and percentage of subjects receiving at least one drug of a particular ATC code and at least one drug in a particular anatomical main group.

Prior medications are defined as drugs taken and stopped prior to first dose of study medication. Any medication given at least once between the day of first dose of randomized study medication and the last day of study visit will be a concomitant medication, including those which were started pre-baseline and continued into the treatment period.

## 9.4 Analysis of the primary variable(s)

The PK Run-in Part will be separately analyzed. The primary objective for the PK Run-in Part is to investigate the pharmacokinetic interaction potential between KAF156 and LUM-SDF. The analyses of PK parameters of KAF156 and LUM-SDF are detailed in [Section 9.5.4](#).

The primary efficacy objective in Part A is to determine the effective dose of KAF156 combined with LUM-SDF given daily over 1, 2, 3 days for treatment of uncomplicated malaria caused by *P. falciparum* in adults/adolescents. If there are multiple KAF156 and LUM-SDF dose combinations that are effective, tolerable and safe, the most effective dose combination(s) in the less frequent 1 to 2 days regimen and the most effective dose combination(s) in the 3 days regimen will be carried over to Part B. Up to 3 KAF156 and LUM-SDF dose combinations may be carried over to Part B.

The primary efficacy objective in Part B is to determine if the selected dose combination regimens from Part A is effective in children down to 2 years.

Data in Part B will be pooled with the corresponding cohort data in Part A to determine which KAF156 and LUM-SDF dose combination can be carried forward to Phase 3 studies.

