## 1.2 Purpose

This Phase 2 study aims to determine the most effective and tolerable dose at the shortest dosing regimen of the investigational drug KAF156 and a Solid Dispersion Formulation of lumefantrine (LUM-SDF) in combination in adult/adolescent and pediatric patients with uncomplicated *P. falciparum* malaria. Different dose combinations and dosing regimens (i.e., 3-, 2-, and 1-day regimens) of KAF156 and LUM-SDF in combination and a reference product Coartem® will be assessed.

This study is set up in a three-part sequential design. Following the PK Run-in Part, Part A of the study will determine in adults and adolescents (greater than or equal to 12 years of age and with a body weight  $\geq 35.0$  kg) the most effective and tolerated dose regimens to be carried forward into Part B which will be conducted in pediatric (2 to < 12 years old and with a body weight  $\geq 10.0$  kg) population. Combined data obtained from Parts A and B will then form the basis for identifying the dose regimen(s) that should be further investigated in Phase 3 development in adults and children down to 2 years of age.

Coartem® will be used as a control for trial sensitivity in Parts A and B so as to evaluate if any significant safety issues or low efficacy results observed in the experimental treatment groups for both adults/adolescents and children are due to treatment or population. It will also provide preliminary relative efficacy for experimental treatment groups compared to the control although it's not statistically powered to show non-inferiority or superiority.

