### Rationale for dose/regimen in Part B:

Upon completion of Part A, all dose cohorts will be evaluated according to the following success/failure criteria:

[figure not shown]

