**Table 3-2 Cohort Success Criteria**

Efficacy	The lower limit of 2-sided 95% exact confidence interval for PCR corrected ACPR at Day 29 is greater than 80%
Safety	A comprehensive assessment of AEs, SAEs, lab data and ECG for investigational and reference product (Coartem ® ) by DMC/Novartis will determine the tolerability success criteria for the cohorts

If needed, secondary efficacy parameters can also be evaluated to discriminate between cohorts in Part A.

Selected cohorts that pass the efficacy/safety hurdles will be further evaluated in Part B.

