#### 9.4.2 Statistical model, hypothesis, and method of analysis

The statistical null hypothesis is that the ACPR rate at Day 29 is at most 80% with the alternative hypothesis that the ACPR rate at Day 29 is greater than 80%. The statistical hypothesis will be evaluated using the lower limit of 2-sided 95% exact confidence interval (CI) (Pearson-Clopperr method) for the ACPR rate at Day 29. If the lower limit of 2-sided 95% exact confidence interval for the ACPR rate at Day 29 is greater than 80%, the null hypothesis will be rejected. The statistical hypothesis testing will be evaluated separately for each KAF156 and LUM-SDF combination in each part based on the PPS. There is no adjustment for multiplicity since this is an exploratory study.

For exploratory purpose, 2-sided 95% confidence intervals for the difference in ACPR at Day 29 between each KAF156/LUM-SDF treatment group and Coartem® will be constructed using the Wilson uncorrected method.

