#### **9.5.1.4 Recrudescence and reinfection**

Reinfection is defined as appearance of asexual parasites after clearance of initial infection with a genotype different from those parasites present at baseline. Reinfection must be confirmed by PCR analysis.

Recrudescence is defined as appearance of asexual parasites after clearance of initial infection with a genotype identical to that of parasites present at baseline. Recrudescence must be confirmed by PCR analysis.

Incidence rates of recrudescence and reinfection at Days 15, 29 and 43 will be estimated by Kaplan-Meier method based on the subset of FAS patients who have clearance of initial infection by Day 7. Time to event (recrudescence or reinfection) will be calculated from the

time of first study medication to the date of first event if a patient experience the event and be censored at the time of last parasite assessment if a patient does not experience the event.

The following additional analyses will be performed for each part and the pooled Part A and Part B:

- For PCR corrected and uncorrected ACPR rates, the 95% confidence intervals for the difference between each test group (KAF156/LUM-SDF combination) and the control (Coartem®) will be provided using the Wilson uncorrected method. For the pooled analysis, the treatment differences versus control will be evaluated using a Mantel-Haenszel estimate of the common risk difference stratified by Part (see SAS manual version 13.2 Pages 2681-2682, 2014).
- For PCT and FCT, the difference between each test group and control will be evaluated using a log-rank test. Patients who did not experience a clearance will be censored at the time of last relevant assessment (parasite or fever). For the pooled analysis, the log-rank test will be stratified by Part.

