2.1 Data analysis general information

Data will be analyzed by Novartis for the interim assessment and after final DBL using SAS version 9.4 according to the data analysis presented in section 9 of the study protocol which is also available in [Appendix 16.1.1 of the CSR](#). Important information is given in the following sections and details are provided, as applicable, in [Appendix 16.1.9 of the CSR](#).

Statistical analyses for PK run-in cohort, Part A, and Part B will be performed separately. For key efficacy and safety outcomes, pooled analysis will be performed by pooling Part B with corresponding cohorts in Part A to determine which KAF156 and LUM-SDF dose combination can be carried forward to Phase 3 studies. Unless described separately otherwise, the same statistical method will be used for separate analysis and pooled analysis.

For each cohort in Part B, a corresponding cohort in Part A will exist with matching dose and regimen. For statistical analyses and clinical study reporting, treatment group name (see [Section 2.1.1](#)), instead of cohort number, will be used for both parts and the pooled analysis which will include only those treatment groups with patients in both parts.

Data analyses required for the study Data Monitoring Committee (DMC) will be analyzed by the third party vendor [REDACTED]. The outline of the DMC analysis plan is presented in the DMC charter and will be detailed in a separate SAP based on this SAP.

Information on visit windowing, imputation rules and the methods of efficacy and safety analyses is given in the sections to follow and details will be provided, as applicable, in [Appendix 16.1.9 of the CSR](#). This SAP covers the methods for: DMC meetings, planned interim analysis, and the final analysis.

Unless otherwise stated, summary tables/figures/listings will be on all patients included in the population under consideration.

Categorical data will be presented as frequencies and percentages. For continuous data, n, mean, standard deviation, median, 25th and 75th percentiles, minimum, and maximum will be presented. Additionally, geometric mean will be presented for PK parameters which may be better described using the lognormal distribution.

Unless otherwise stated, p-values will be provided for two-sided alternative hypotheses and presented up to 4 significant digits after decimal place; confidence intervals will be presented up to 2 significant digits after decimal place.

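### Is a rule needed for a regimen that misses its Part B test in children but looks good on pooled Part A and Part B data?

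*Protocol*

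**What the plan says.** Three places link the Phase 3 choice to both parts together. Protocol 1.2 names the combined Part A and Part B data as the basis for choosing regimens for further study in adults and in children from the age of 2. Protocol 9.4 says "Data in Part B will be pooled with the corresponding cohort data in Part A to determine which KAF156 and LUM-SDF dose combination" moves on. SAP 2.1 describes "pooling Part B with corresponding cohorts in Part A to determine which KAF156 and LUM-SDF dose combination can be carried forward to Phase 3".

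The formal inference is set per part. Protocol 9.4 states: "The primary efficacy objective in Part B is to determine if the selected dose combination regimens from Part A is effective in children". Protocol 9.4.2 states: "The statistical hypothesis testing will be evaluated separately for each KAF156 and LUM-SDF combination in each part based on the PPS", and SAP 2.5.2 says the same. The null hypothesis of a rate of at most 80% is rejected when the exact 95% lower limit exceeds 80%. Protocol 9.8 sizes Part B for this test, at 42 per-protocol patients per combination.

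A written criterion exists for the earlier step. Protocol 3.3 says: "Upon completion of Part A, all dose cohorts will be evaluated according to the following success/failure criteria", and Table 3-2 applies the same 80% lower-limit rule to decide entry to Part B. No counterpart is given for the step from Part B to Phase 3.

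The pooled comparisons appear with the secondary variables. Protocol 9.5.1.4 introduces them with: "The following additional analyses will be performed for each part and the pooled Part A and Part B". SAP 2.7.2.6 gives a Mantel-Haenszel difference versus Coartem stratified by part, stratified log-rank tests, and descriptive summaries of the Day 29 response by age and weight group. None carries a threshold.

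**The concern.** In Protocol 9.4 two sentences stand next to each other. One says Part B settles whether the regimens work in children; the next says pooled data settle what goes to Phase 3. A regimen could miss its test in children and still show a good pooled rate, carried by adults. The adult data in the pool also lean upward, because a cohort reaches Part B only after passing the Part A hurdle. If nothing fixes beforehand which reading counts, the more favourable one could be chosen afterwards, and a regimen that is weak in children could go forward on the strength of adult results.

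**Working it through.** **Inputs.** Null rate 80%, exact 95% lower-limit rule, per-protocol set (Protocol 9.4.2). Target 42 per combination, design rate 95%, power stated as at least 80% (Protocol 9.8). Up to three combinations in Part B (Protocol 3.1).

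**The plan's own figure.** The Clopper-Pearson lower limit is 77.4% for 38/42 and 80.5% for 39/42, so the pass mark is 39. Power at a true rate of 95% is P(X ≥ 39 | 42, 0.95) = 84.3%, which agrees with the stated 80% or more. The number randomized follows as 42/(1 − 0.16) = 50.

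**How often Part B misses.** Miss = P(X ≤ 38 | 42, p). At least one of k independent regimens with a common rate: 1 − (1 − miss)^k.

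| True rate in children | One regimen | At least one of 2 | At least one of 3 |
|---|---|---|---|
| 95% | 15.7% | 28.9% | 40.1% |
| 93% | 33.9% | 56.3% | 71.1% |
| 90% | 61.6% | 85.3% | 94.3% |

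Over an assumed range of 38 to 48 evaluable children per arm, the single-regimen figures run 9–32%, 24–54% and 53–78%. These are 1 minus power at rates that are effective by the plan's own standard of more than 80%. Each such miss is a false negative, and a favourable pooled result alongside it points the right way. The table shows that a miss is plausible; it does not measure harm.

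**How often the two readings would conflict.** The plan states no pooled pass mark, so this is illustration only. Suppose the 80% rule were applied to 42 + 42 patients. The lower limit is 79.2% for 74/84 and 80.6% for 75/84, so the mark would be 75. Take a true adult rate of 95% and a Part A pass (39 or more of 42):

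| True rate in children | Part B misses | Misses and pooled passes | Share of misses in which pooled also fails |
|---|---|---|---|
| 80% | 97.9% | 41% | 58% |
| 85% | 89.3% | 63% | 29% |
| 90% | 61.6% | 56% | 9% |
| 95% | 15.7% | 16% | 1% |

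The last column is 1 minus the conditional chance that the pooled result passes given a miss (42.1%, 70.8%, 91.4%, 99.1%). So a missed Part B test is not always a conflict, least often where the rate in children is poorest.

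**What a reader would see.** With 41/42 in Part A and 36/42 in Part B, the report shows 85.7% in children (95% CI 71.5 to 94.6, null not rejected) and 91.7% pooled (83.6 to 96.6).

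**Which reading governs.** There are two questions.

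1. *Is the regimen effective in children?* Protocol 9.4 assigns this to Part B, 9.4.2 and SAP 2.5.2 give the rejection rule, and 9.8 sizes the sample for it. No pooled hypothesis is stated. SAP 2.5, on the primary objective, does not repeat the pooling sentence. If the Part B lower limit is 80% or less, the null for children stands whatever the pool shows.
2. *Which regimen should be studied next?* This is a development decision for a Phase 3 programme in adults and children, so using both populations is natural. The earlier step from Part A to Part B is also partly judgement: Table 3-2 leaves safety to a comprehensive assessment, Protocol 3.3 allows secondary efficacy parameters to separate cohorts, and 9.8 allows PK/PD modelling to assist.

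**The case for a change.** The strongest case for a change is that the silence is real and falls where adult data could mask a weak result in children. Under the illustrative rule, a regimen whose true rate in children is only 80%, the null value, would miss Part B and still pass on pooled data 41% of the time (36% to 54% for true adult rates of 93% to 98%). Stratifying the Mantel-Haenszel estimate by part does not help: it yields one common difference versus Coartem and sets no threshold for children. Exploratory status explains the lack of multiplicity adjustment, but it does not explain why the two readings are left unranked.

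Two things stand: no sentence covers the conflict, and prior selection in Part A tilts the pooled rate upward. The rest carries less weight. The 41% depends on a pooled pass mark that the plan does not contain. The Part B rate, interval and test outcome are reported in any case, so a weak result in children cannot be hidden by the pool. A favourable pooled result leads to further study, not to an efficacy claim in children. Stating that Part B governs conclusions in children would repeat Protocol 9.4 and 9.4.2. Showing pooled and per-part comparisons together is largely planned already. A note on how results were weighed would only be a record. The SAP's revision history also has an entry made after the final database lock, so a sentence added to that version would no longer be prospective.

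**Conclusion.** The plan does not say how the Phase 3 choice treats a regimen that misses in Part B and looks good when pooled. This is missing detail in an exploratory study, and filling it would bring no gain. The conclusion about children already rests on the Part B per-protocol test, and the pooled comparisons are secondary. The chance of a miss, 16% at a true rate of 95% rising to 62% at 90%, assumes 42 evaluable children per regimen; the figures for two or three regimens further assume independent arms at a common rate. A clarifying sentence would do no harm, but it would change no estimate, no test, no power figure and no regimen's chance of going forward. No change to the plan is called for.
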